## **12.7.3 Exploratory Analysis**

### **12.7.3.1 Questionnaires**

#### **12.7.3.1.1 FTND Questionnaire**

The FTND (Section 7.2.1 "Fagerström Test for Nicotine Dependence (FTND)") score, the number and percent of subjects in each category of the FTND score (Mild/ Moderate/ Severe) and the response to the first item of the FTND ("Within 5 minutes", "6 to 30 minutes", "31 to 60 minutes", "After 60 minutes") will be summarized and listed at V1, V10 and V16 (Listing 15.3.5.1; Tables 15.2.4.13.1 and 15.2.4.13.2).

The change from V1 in the FTND score category and response to the first item of the FTND will be presented in a shift table.

All summaries and shift tables will be performed on the FAS-EX (using the product use pattern category) and PP population.

#### **12.7.3.1.2 Intent to Use THS 2.2 Questionnaire**

Baseline for the Intent to Use Questionnaire is the assessment collected at Visit 4 since this is the only pre-randomization collection. The shift from Baseline will be calculated for each item of the ITUQ (Section 7.2.5 "Intent to Use THS 2.2 Questionnaire") at V10 and V16. Item scores and shift from Baseline will be summarized by product use category and listed (Listing 15.3.5.2; Tables 15.2.4.14.1 and 15.2.4.14.2). For items 1-6, the shifts will be presented using the categories of 'Positive intention' and 'Not positive intention' as defined in Section 7.2.5 "Intent to Use THS 2.2 Questionnaire".

All summaries will be performed on the FAS-EX and PP populations.

### **12.7.3.2 Exposure/Response and Effect of Dual-Use on Smokers'**

#### **Health Profile**

To describe the effect of dual-use on the components of the "smokers' health profile" the exposure-response relationship between the CC, THS 2.2 exposure and the "smokers' health profile" endpoints level will be evaluated by means of a propensity score approach, based on the method proposed by Follmann [23].

This approach aims to estimate the effect of THS 2.2 among those subjects who would adhere to the THS 2.2, using an ITT-type approach. It is based on the assumption that the subject's propensity to adhere to THS 2.2 could be estimated based on baseline covariates, and that randomization ensures that the overall population of subjects who would adhere to

THS 2.2 will be about the same in the two arms, even though this proportion is unobservable in the CC arm. Also by randomization, any relationship between product adherence and baseline covariates observed in the THS arm would be about the same in the CC arm, had the latter group been randomized to the THS 2.2 product.

The analysis will be performed in a two-step process. First a propensity score (PS) model is developed on the FAS-AR using baseline covariates to predict adherence to THS 2.2 as observed in the THS-use pattern category (JV4, V16[]) in the THS 2.2 arm, by means of a logistic regression model.

```
proc logistic data = _THSarmData_ ;  
model product_use(event='THS-use') = <model terms> /  
stepwise=selection slentry=0.157 slstay=0.157 ;  
run;
```

The following variables will be considered for their inclusion in the model by means of the stepwise selection method with entry and removal alpha levels of 15.7%, which approximately corresponds to the use of the Akaike Information Criterion [24]:

- Demographics and baseline characteristics (see Table 15.2.1.4.3).
- ITUQ items (items 1 to 6 will use the mapped categories of 'Positive intention' and 'Not positive intention' while item 7 will use the original 6-point scale).
- SES sub-scores (educational attainment and annual household income).
- Baseline of all primary endpoints and Neq; for sICAM-1, 11-DTX-B2, 8-epi-PGF2 $\alpha$ , COHb, Total NNAL, and Neq, the value will be natural log-transformed while HDL-C, WBC, and FEV1 will be analyzed in the original scale.

In case of missing baseline data, the median of non-missing baseline values across all FAS-AR subjects in the THS 2.2 arm will be imputed for each continuous variable and the mode of non-missing baseline values across all FAS-AR subjects in the THS 2.2 arm will be imputed for each categorical variable.

The final model will be fit using the following SAS code. Goodness of fit diagnostics and discrimination ability of the fitted model based on the area of the receiver operating curve will be provided in statistical output listings.

```
proc logistic data = _THSarmData_ outmodel=_psmodel_ ;  
model product_use(event='THS-use') = <model terms> /  
clodds=wald lackfit outroc = ps_r ;
```

```
output out= ps_p XBETA=ps_xb STDXBETA= ps_sdxs PREDICTED =  
ps_pred;  
run;
```

The variables included in the final PS model together with the odds ratios and 95% CIs will be tabulated (Table 15.2.4.16). The fitted model is used to predict scores on both the THS 2.2 and CC arms, using the following SAS code:

```
proc logistic inmodel=_psmodel_;  
score data = _alldata_ out=_predData_;  
run;
```

In case of missing values in covariates included in the final PS model, the same imputation approach used for PS model fitting will be adopted. For the scoring of subjects in the CC arm, the median and mode values used for imputation will be derived only from subjects in the CC arm of FAS-AR. Histograms of the predicted PS scores will be presented by randomization arm (Figure 15.1.2.1) and individual PS scores will be reported in the statistical output listings.

The second step consists of a MMRM model analysis conducted on the FAS-AR with the model terms noted below (including the same adjustment covariates used for the primary analysis - see Section 12.7.1.2 “Smokers’ Health Profile Endpoints Evaluation”) and including the interaction of predicted PS values fit as a natural cubic spline with the randomization arm and the interaction of predicted PS values fit as a natural cubic spline with visit (Table 15.2.4.17). The THS 2.2 vs CC effect at V10 and V16 will be tabulated for PS levels equal to 100%, 75%, 50%, and 25% and displayed as a forest plot (Figure 15.1.2.2). A PS\*randomization arm interaction p-value (via the spline interaction) of 15.7% or less will be considered as indicative of a statistically significant THS effect based on the level of adherence to THS.

The SAS code for the mixed model to be used is shown below:

```
Proc glimmix data=_data_ method=rspl maxopt=200;  
Class subject rand_arm site sex caucasian_origin visit;  
Effect spl = spline(P_THS-use / naturalcubic);  
Model endpoint = baseline sex caucasian_origin rand_arm spl  
visit baseline*visit rand_arm*visit visit*spl  
rand_arm*spl <covariates> / ddfm=kr;  
Nloptions technique=nrridg;  
Random site;  
random visit / subject=subject type=un residual;  
Lsmeans rand_arm*visit / at P_THS-use=xxx slice=visit  
alpha=0.05 diff cl pdiff;  
Run;
```

where P\_THS-use=xxx is set to the 1, 0.75, 0.5, 0.25 for each PS level. Note that ‘method=rspl’ is equivalent to using ‘method=reml’ with proc mixed. Also, ‘nloptions technique=nrridg’ solves the iterative optimization problem by means of a ridge-stabilized Newton-Raphson algorithm as used by proc mixed. In case of model convergence issues, this will be reported in the study report and additional covariance structures will be investigated with the following order: heterogeneous compound symmetry (type=csh), heterogeneous toeplitz (type=toeph), heterogeneous autoregressive (1) (type=arh(1)), and variance components (type=vc).

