#### **12.7.1.3.2 FAS-AR Sensitivity Analysis**

A sensitivity analysis will be conducted on the “smokers’ health profile” endpoints for the FAS-AR (Table 15.2.3.2.3) using a 95% CI and 2-sided p-value to compare the THS 2.2 and CC arms. Subjects will be analyzed as randomized by means of a MMRM model including the same adjustment covariates used for the primary analysis (see Section 12.7.1.2 Smokers’ Health Profile Endpoints Evaluation”), except that randomization arm will be used instead of product use category. The FAS-AR results will be interpreted taking into account those observed from the sensitivity analysis described in Section 12.7.3.2 “Exposure/Response and Effect of Dual-Use on Smokers’ Health Profile”.

Forest plots of THS 2.2 versus CC arms will be displayed at V7, V10, and V16 for the FAS-AR (Figure 15.1.1.3).

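### SAP 12.7.3.2 scores the THS arm in-sample and the CC arm out-of-sample, so self-selection can re-enter the adherence analysis when adherence and endpoint are related beyond the baseline covariates

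*SAP*

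**What the plan says.** The analysis in SAP 12.7.3.2 has two steps.

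Step 1 is a logistic model to "predict adherence to THS 2.2 as observed in the THS-use pattern category" over the 12 months in the THS 2.2 arm. Terms are chosen by a "stepwise selection method with entry and removal alpha levels of 15.7" per cent. Candidates are demographics and baseline characteristics, the intent-to-use items, two socio-economic sub-scores, and "Baseline of all primary endpoints and Neq". The final fit uses the same arm: "proc logistic data = _THSarmData_ outmodel=_psmodel". After that, "The fitted model is used to predict scores on both the THS 2.2 and CC arms". The section specifies no hold-out, cross-fitting, shrinkage or bootstrap, and the planned area under the ROC curve comes from the data used for fitting.

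The justification is randomization: "any relationship between product adherence and baseline covariates observed in the THS arm would be about the same in the CC arm".

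Step 2 is a repeated-measures model on the FAS-AR with the score as a natural cubic spline, interacting with arm and with visit. THS 2.2 versus CC is tabulated at scores of 100, 75, 50 and 25%, and an "interaction p-value (via the spline interaction) of 15.7% or less will be considered as indicative of a statistically significant THS effect" by level of adherence.

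The section is labelled exploratory, but SAP 12.7.1.3.2 states: "The FAS-AR results will be interpreted taking into account those observed from the sensitivity analysis described in Section 12.7.3.2". Appendix 16.2 also lists it among the analyses that support interpretation of the primary objective.

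**The concern.** The randomization argument holds for the true relation between baseline covariates and adherence. It does not hold for a score that was selected and fitted on one arm's realised adherence. In the THS arm, part of each subject's score is chance fit to whether that subject did become a THS user. No such component can exist in the CC arm. Two subjects with the same score, one per arm, are then not comparable: the THS subject is more likely to be an actual adherer than the covariates justify.

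If adherers differ on the endpoint for reasons outside the covariates, the THS-arm score carries that difference and the CC-arm score does not. The THS-versus-CC contrast is then tilted across score levels even when the product does nothing. At stake is the one analysis meant to give an adherer effect protected by randomization, and the way the randomized FAS-AR result is read through it.

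**Working it through.** **1. The plan's own figure.** The 15.7% level is the AIC equivalent for one parameter: P(chi-square, 1 df > 2) = 0.1573. It reproduces.

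**2. Inputs from the documents.** 475 randomized per arm, 20% drop-out or insufficient product-use data, and about 60% THS-use in the THS arm (SAP 8): 475 × 0.80 = 380 per arm. Candidates: 7 intent-to-use items + 2 socio-economic sub-scores + 8 primary endpoints + Neq = 18. SAP 12.3 ties baseline comparability to the Table 3 covariates, which are 12 distinct variables, so about 30. The simulation used 31, and 45 as an upper value if factors are expanded to dummies.

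**3. Input that must be assumed.** This is the residual correlation (rho) between latent adherence tendency and endpoint, given baseline covariates. The range taken is 0 to 0.5. At 60% adherence the implied gap between adherers and others is rho × 0.386/(0.6 × 0.4) = 1.61 × rho. That is 0.48 SD at rho 0.3 and 0.80 SD at rho 0.5.

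**4. Simulation with no THS effect for anyone.** Stepwise logistic regression (0.157/0.157) in the THS arm, both arms scored, then a baseline-adjusted endpoint at one visit on arm, score and arm × score. There were two weak true predictors and 2,000 trials per row. The Monte Carlo standard error at the nominal rate is sqrt(0.157 × 0.843/2000) = 0.8 points.

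| rho | Planned, linear | Planned, spline | Cross-fitted, one split | Score from independent sample | False effect (SD), planned linear, at 100/75/50/25% |
|---|---|---|---|---|---|
| 0 | 15.8% | not run | 16.5% | 14.9% | about 0 throughout |
| 0.3 | 22.1% | 19.6% | 17.5% | 14.8% | +0.10/+0.04/-0.03/-0.09 |
| 0.5 | 31.5% | 27.5% | 17.2% | 15.3% | +0.17/+0.06/-0.04/-0.15 |

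The percentages are rejection rates at the 15.7% rule. A second simulation with the same settings (linear score) gave about 15%, 19% and 29%, with about 0.08 and 0.14 SD at score 100%. One-split cross-fitting there gave 15-16% and near-zero bias.

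**5. Mechanism.** The score's AUC for adherence is 0.678 in the THS arm and 0.587 in the CC arm. With a score from an independent sample, the rule keeps its level. So the excess comes from scoring the THS arm in-sample, not from estimation error in the score as such.

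**6. Intervals.** The 95% CI at score 100% excludes zero in the direction of the bias in 7.9% (rho 0.3) and 13.8% (rho 0.5) of trials, against 2.5% nominal.

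**7. Scale for FEV1.** If the SAP's SD of 6.4 %pred is taken as the residual SD, score 100% carries 6.4 × 0.08 to 6.4 × 0.103 = 0.5 to 0.7 %pred at rho 0.3, and 6.4 × 0.14 to 6.4 × 0.168 = 0.9 to 1.1 at rho 0.5. The target precision is ±1.5.

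**8. Sensitivity.** With 45 candidates: 24.6% and 37.3%. With four fair predictors at rho 0.3: 20.5% and 0.05 SD at score 100%. With no true predictors and 309 per arm (475 × 0.65): 25.3% and 41.4%. At rho 0.1, with 309 or 475 per arm: 15-18%.

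**9. Repeated splits.** With uninformative covariates at rho 0.5, averaging the scores over splits reversed the bias and rejected in 21-25% of trials. Averaging the step-2 estimates did not reverse it.

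The simulations use one visit and independent normal covariates. They omit the SAP's arm-specific median and mode imputation, which is a further difference between the arms.

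**The case against.** The bias needs adherence to be related to the endpoint after baseline adjustment. With none, the rule keeps its level, and no document gives the correlation. This stands, and the size can only be stated as a range. The condition is plausible, though: Appendix 16.2 itself attributes product use to social, cultural and psychological drivers, many of which are not candidates.

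The candidates include pre-randomization intention items, which may predict adherence well, and the SAP uses a spline. Both reduce the inflation. Contrasts at low scores may also lie almost outside the data: in one run with uninformative covariates, about 0.5% of THS subjects scored below 30%. These points stand as limits on size.

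The section is exploratory, the study has no formal hypotheses, and the two tables (15.2.4.16 and 15.2.4.17) are not flagged for topline or registry reporting. This lowers the priority but does not remove the point, because the SAP commits to reading FAS-AR in the light of this analysis.

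A reader might infer that the analysis is biased toward the as-exposed answer in general. That does not follow. The error is a tilt, with opposite signs at high and low scores, and it favours THS only if adherers have better outcomes. Nor is cross-fitting uniformly better. With a real 1 SD effect in adherers and no residual correlation, the effect at score 100% should be 1.0 SD in size. The in-sample score gave about -1.0 and the cross-fitted score about -0.78.

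**Conclusion.** The concern holds conditionally. The scoring asymmetry is explicit in the SAP, and randomization does not protect a score fitted in-sample in one arm only. With no THS effect, two weak predictors, a linear score and 380 per arm, rejection at the 15.7% rule is nominal at residual correlation 0, about 19-22% at 0.3 and about 29-32% at 0.5. The false effect at score 100% is about 0.08-0.10 SD at 0.3 and 0.14-0.17 SD at 0.5. It is larger if baseline data do not predict adherence, and smaller with good predictors or the spline.

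A reader might also infer that the main results are compromised. They are not: the plain FAS-AR contrast and the primary FAS-EX estimate do not use this score. Nor do the documents support treating a very large inflation as expected, since that requires baseline covariates that predict nothing together with a strong residual correlation.

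**What to change.** Amend SAP 12.7.3.2 before database lock:

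- Split the THS arm into 10 random folds. Repeat the stepwise selection and fit without each fold, and score each THS subject with the model that excluded that subject.
- Split the CC arm into 10 random folds and score each with the matching fold model.
- If splits are repeated, average the step-2 estimates, not the scores.
- Base the interaction p-value, and any use of this analysis to interpret FAS-AR, on the cross-fitted version. Show the planned in-sample version beside it.
- If both steps are bootstrapped for the intervals, keep all copies of a subject in the same fold. Otherwise the leak returns.
- Check and report calibration of the cross-fitted score in the THS arm.

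The cost is SAP wording and a real programming load (repeated selection around the mixed model for eight endpoints), with no new data. The price is wider intervals and a flattened gradient at extreme scores when a real effect exists, which is why calibration should be reported.

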4.2 Rationale for Study Design and Control Groups

The extension study will be conducted as a follow-up of the randomized exposure period of the original study extending the exposure from V10 (Week 26) to V16 (Week 52).

In conjunction with the original study, this extension study will:

- Provide a perspective of product usage in a “real world setting” over a 52 week period, where smoking CC in addition to THS 2.2 is expected (dual use).
- Determine the changes in the components of the “smokers’ health profile” upon THS 2.2 use over a 52 week period. A particular interest will be given to FEV₁, one of the endpoints of the “smokers’ health profile”, for which a time frame of 6 months to 3 years is expected to observe a favorable change. Additional clinical risk endpoints involved in the mechanism of smoking-related diseases will be studied to provide additional scientific evidence to strengthen the primary objective.

The “smokers’ health profile” (Table 1), and used as co-primary endpoints in the original study, is a collection of eight, broad-ranging clinical risk endpoints, that together cover the biological processes, physiological systems, and mechanisms of actions that are known to contribute to smoking-related diseases. Many of the clinical risk endpoints included within the “smokers’ health profile” are also mentioned in the 2010 Surgeon General's Report “How

Confidentiality Statement

Data and information contained in this document are considered to constitute trade secrets and confidential commercial information, and the legal protections provided to such trade secrets and confidential information are hereby claimed under the provisions of applicable law. No part of this document may be publicly disclosed without the written consent of Philip Morris Products S.A.

Tobacco Smoke Causes Disease: The Biology and Behavioral Basis for Smoking-Attributable Disease” [5].

Twenty four-hour urine is the standard method to measure the levels of excretion of BoExp and will be collected in this study.

This study is designed as an *ad libitum* study without product use restriction in order to mimic as close as possible “real life” conditions.

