12.5.4 Confirmatory Analysis

No formal confirmatory analysis is foreseen in this study.

FEV₁, HDL-C, and WBC will be analyzed in the real scale. Other clinical risk endpoints, which will be analyzed in the logarithmic scale, will be back-transformed to provide relative effects.

The primary analysis for the “smokers’ health profile” endpoints will be based on a mixed model for repeated measurements (MMRM). The model will include the endpoint value as the dependent variable, product use pattern category, visit (V7, V10, and V16), and exposure by visit interaction as fixed effects, with adjustment for site, sex, and Baseline endpoint value. In order to adjust for potential residual confounding, covariates found to be not balanced between THS-use and CC-use will be included in the final model. Modeling assumptions will be evaluated and model fit assessed by the analysis of residuals (model diagnostics) and by comparing the values predicted versus the observed endpoint values (calibration).

The point and interval estimate of the contrast of THS-use versus CC-use at V16 will be tabulated for the FAS-EX.

Supportive analysis will be conducted on the FAS-AR and PP set.

The detailed analysis methods, including subgroup analyses, are given in the SAP.

Confidentiality Statement

Data and information contained in this document are considered to constitute trade secrets and confidential commercial information, and the legal protections provided to such trade secrets and confidential information are hereby claimed under the provisions of applicable law. No part of this document may be publicly disclosed without the written consent of Philip Morris Products S.A.

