### 10.1 Full Analysis Set - As Randomized (FAS-AR)

The FAS-AR consists of all the randomized subjects with signed ICF who have both a valid baseline and at least one valid post-randomization value for one of the primary endpoints collected at V7, V10, or V16.

Subjects enrolled at sites that are terminated due to findings of non-compliance with good clinical practice (GCP) and/or with the protocol will be excluded from the FAS-AR.

Subjects included in the FAS-AR are analyzed as per randomized arm.

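### The step-2 propensity model assumes the same effect-by-adherence gradient at V7, V10 and V16, so the Week 52 rows by score level rest mostly on Month 3 and Month 6 data

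*SAP*

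**What the plan says.** SAP 12.7.3.2 fits a two-step propensity analysis on the FAS-AR. Step 1 predicts the 12-month THS-use category from baseline data in the THS 2.2 arm and scores both arms. Step 2 is a repeated-measures model. Its code contains "visit baseline*visit rand_arm*visit visit*spl" followed by "rand_arm*spl <covariates> / ddfm=kr", and its residual structure is "random visit / subject=subject type=un residual". The text lists the same terms, "including the interaction of predicted PS values fit as a natural cubic spline with the randomization arm" and the score-by-visit interaction, so the code is not a slip. Neither contains `rand_arm*visit*spl`.

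The reporting plan is "The THS 2.2 vs CC effect at V10 and V16 will be tabulated for PS levels equal to 100%, 75%, 50%, and 25" (percent), with a forest plot. A single arm-by-score p-value of 15.7% or less is read as showing that the effect depends on adherence.

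The step-2 text does not restate which visits enter. The primary model on which it is built uses "visit (V7, V10, and V16), and exposure by visit interaction as fixed effects" (Protocol 12.5.4). The FAS-AR requires "at least one valid post-randomization value for one of the primary endpoints collected at V7, V10, or V16", so it keeps subjects with no V16 value.

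**The concern.** With these terms the arm effect at visit v and score p is a_v + g(p), with one g for all visits. Whatever the data show, the difference between the 100% and 25% rows must be the same at V10 and V16. The table therefore cannot show the adherence gradient changing between Week 26 and Week 52, which is the interval the extension adds.

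Protocol 4.2 gives particular interest to FEV1, "for which a time frame of 6 months to 3 years is expected to observe a favorable change". An effect that scales with adherence and is still growing has a growing gradient.

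The 100% row is the effect in would-be adherers that the method aims to estimate. SAP 12.7.1.3.2 says the FAS-AR results will be interpreted in the light of this analysis, and SAP 16.2 names it among the supports for the as-exposed primary analysis.

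**Working it through.** **What the plan gives.** It states no share of borrowing between visits, no within-subject correlation, no SD by visit, no FAS-AR count by visit and no score distribution. From SAP 8 come 475 randomized per arm, 65% of randomized subjects enrolled in the extension, about 60% THS-use in the THS 2.2 arm, and an FEV1 SD of 6.4 %pred. The plan's own precision claim reproduces from these inputs: 475 × 0.65 = 308.75 in CC-use, × 0.60 = 185.25 in THS-use, and a half-width of 1.96 × 6.4 × √(1/185.25 + 1/308.75) = 1.17 %pred, inside ±1.5. The 15.7% level is P(χ² on 1 df > 2) = 0.157.

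**Weights on each visit's gradient.** The shared gradient is estimated by w′g, where g holds the true visit gradients, w = M1/(1′M1), and M = n_A Σ₃⁻¹ + n_B Σ₂⁻¹ for subjects with and without V16. Assume equal SDs, compound symmetry with correlation ρ, and V16 data on 65% of the V7/V10 subjects. Then:

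- V7 and V10 each have weight proportional to 0.65/(1+2ρ) + 0.35/(1+ρ).
- V16 has weight proportional to 0.65/(1+2ρ).

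| ρ | V7, V10 (each) | V16 | normalised V16 | share from V7 and V10 |
|---|---|---|---|---|
| 0 | 1.000 | 0.650 | 0.245 | 75.5% |
| 0.5 | 0.558 | 0.325 | 0.225 | 77.5% |
| 0.7 | 0.477 | 0.271 | 0.221 | 77.9% |

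Other assumptions move the share:

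- 66.7% with no V16 loss (compound symmetry)
- 71-73% with 760 subjects at V7/V10 and 617 at V16
- 79-83% with 950 and 494
- 55-77% under AR(1) correlation 0.5-0.8
- 44-63% if the V16 SD is 20% lower, and 86-99% if it is 20% higher (ρ 0.3-0.7)

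**Bias at V16.** Near the mean score (assumed 0.6, Beta(3,2)) `rand_arm*visit` fits the V16 effect correctly. Away from it, the fitted effect is roughly the mean-score effect plus (p − 0.6) times the pooled gradient. Effects below are fractions of the V16 full-adherence effect.

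| Scenario | 25% | 50% | 75% | 100% |
|---|---|---|---|---|
| Truth at V16 | 0.25 | 0.50 | 0.75 | 1.00 |
| Gradient 0, 0.5, 1 over V7, V10, V16 (ρ 0.5) | 0.45 | 0.56 | 0.66 | 0.77 |
| Gradient 0.25, 0.5, 1 (ρ 0.7) | 0.42 | 0.55 | 0.68 | 0.80 |
| Gradient 1, 1, 1 (plateau by V7) | 0.25 | 0.50 | 0.75 | 1.00 |

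For the first scenario at ρ 0.5, the pooled gradient is 0.387 × 0 + 0.387 × 0.5 + 0.225 × 1 = 0.419, and 0.6 + 0.4 × 0.419 = 0.77. In a further case, the average effect rises 0.2, 0.5, 1.0 over visits with a constant score gradient; the bias is zero at every score.

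**FEV1 scale.** If the ±1.5 margin is 75% of the anticipated effect (SAP 5.4.2), that effect is 1.5/0.75 = 2.0 %pred, a figure the documents do not state. The first scenario then reads about 0.9, 1.1, 1.3 and 1.5 %pred at 25, 50, 75 and 100%, against 0.5, 1.0, 1.5 and 2.0.

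**With the three-way term.** The V16 effect is recovered exactly in every scenario tried. With 475 per arm and a linear score, the SE at score 100% rises from 0.138 to 0.162 SD (17%) at ρ 0.7 and from 0.126 to 0.176 SD (40%) at ρ 0.3. With a spline the rise is about 20-50%. At score 0.6 the linear SE is unchanged (0.072 SD at ρ 0.7).

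**The case against.** Sharing one gradient is a defensible trade of bias for variance. In the first FEV1 scenario the bias at 100% is about −0.47 %pred, but the SE is 0.80-0.88 (linear score, ρ 0.3-0.7), giving a root mean squared error of √(0.80² + 0.47²) = 0.93 to √(0.88² + 0.47²) = 1.00. With the term added the bias goes, but the SE alone is 1.03-1.12. This stands: the visit-specific fit removes a bias but does not promise a more accurate estimate, so it belongs beside the pooled fit and not in its place.

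It also stands that the gradient need not change for most endpoints. Protocol Table 1 lists six of the eight as reversing within 3 months or sooner, and only FEV1 and WBC within 6-12 months. Nor does the Week 52 question depend on this model, because the primary, per-protocol and FAS-AR models all give visit-specific effects.

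A reader might infer that the Week 52 rows are wrong for every endpoint whose effect changes over time. The documents do not support that: `rand_arm*visit` is in the model and absorbs any change that is uniform across scores. A reader might also take 78% as a property of the plan. It is not: it needs an assumed correlation, equal SDs, compound symmetry and a V16 count of 65% of V7/V10, whereas the SAP specifies an unstructured covariance and its 65% is a share of randomized subjects.

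**Conclusion.** The model imposes an undiscussed assumption: a common arm-by-score gradient at V7, V10 and V16. That follows from the listed terms alone. Its consequence is that the V16 rows take most of their gradient from earlier visits, about 55-83% with equal SDs and a wider range otherwise.

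Bias arises only where the gradient itself changes between visits, which is plausible mainly for FEV1 and WBC. It could reach a fast-responding endpoint if low-score subjects drift back to cigarettes during the year, but the documents give no data on that. The 100% and 25% rows carry the distortion: in the scenarios above, 20-23% of the full effect too low at 100% and 17-20% too high at 25%.

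These sizes rest on assumed correlations, SDs, visit counts, a mean score of 0.6, V16 missingness unrelated to score, and the chosen time courses. The analysis is exploratory and the primary THS-use versus CC-use estimate is untouched.

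**What to change.** Also fit step 2 with `rand_arm*visit*score`, using a linear score or few knots for stability, at least for FEV1 and WBC. Report the V10 and V16 effects at each score level from these visit-specific gradients beside the pooled ones. State in SAP 12.7.3.2 that the pooled rows assume a common gradient and that the 15.7% arm-by-score test refers to that pooled gradient, since it is not a test at V16.

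The cost is one extra fit per endpoint and wider intervals at the extreme scores: an SE roughly 17-50% larger at score 100%, with little change near the mean score.
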